# STUDY SUMMARY

Study Title	Impact of systematic user testing of written guidance on the
	rate of moderate to severe errors made by hospital nurses
	during in situ simulation of the preparation and administration
	of an intravenous medicine: phase 2 – in situ simulation
Short title	Effects of user testing injectable medicines guidance – phase
	2
Study Design	Single-blind, randomised parallel group in situ simulation
	experiment
Study Participants	Qualified nurses or midwives registered with the Nursing and
	Midwifery Council, who are authorised to prepare and
	administer intravenous medicines in a hospital and who have
	done this during at least 50% of working shifts during the past
	six months (or since authorisation to prepare and administer
	intravenous medicines if this was granted more recently).
Planned Size of Sample (if applicable)	121-172 participants per group
Follow up duration (if applicable)	N/A
Planned Study Period	October 2018 to July 2019
Research Question/Aim(s)	Research question (whole study): Is it possible to reduce the
	incidence of medication errors by improving the content,
	wording, structure and formatting of written documents
	providing technical information to health professionals?
	Objectives for the entire study are:
	1. To identify and resolve problems in a typical NHS
	Injectable Medicines Guide (IMG) monograph using
	systematic user testing.
	2. To compare the rates of preparation and administration
	errors associated with use of the original and user
	testing developed IMG monograph.
	3. To determine whether systematic user testing of the
	IMG is a cost-effective approach to improving patient
	safety.
	4. To advise the IMG Advisory Board on generic lessons
	learned during user testing that could be introduced to
	the entire guide during the next revision cycle.
	Only objective 2 will be addressed during phase 2 of the
	study (this protocol).

## ROLE OF STUDY SPONSOR AND FUNDER

The funder had/will have no influence on the design, conduct, data analysis and interpretation, manuscript writing and dissemination of results associated with this study. The sponsor had/will have final approval on the design and conduct of this study, but no influence on the data analysis and interpretation, manuscript writing and dissemination of results associated with this study.

# ROLES AND RESPONSIBILITIES OF STUDY MANAGEMENT COMMITEES/GROUPS & INDIVIDUALS

## **Study Advisory Group**

A Study Advisory Group has been established to:

- Provide advice and support
- Provide advice on current NHS priorities in this area
- Provide advice on current NHS practice in this area
- Oversee the completion of the project in accordance with the principles of Good Clinical Practice
- Advise and assist with dissemination of findings to NHS stakeholders

The group is made up of practising nurses, pharmacists and doctors with expertise in medicines safety and the administration of injectable medicines. This group can be considered independent of the investigators and sponsor, as it will chaired by a member who is not a researcher or employed by the sponsoring or funding organisations.

As the participants in this study will be NHS nurses, members of the Study Advisory Group will also play a participant involvement role, by providing advice on study design, study documentation and recruitment. Additional advice on study document design and recruitment will also be sought from independent nurses.

## Lay Advisors

Two lay advisors will be recruited to assist with the dissemination of the findings of this study to a lay audience. They will be invited to observe user testing and the *in situ* simulation phases of this study and to share their experiences via suitable lay forums. They will also assist with the dissemination of the final results of the study to a lay audience.

**KEY WORDS:** 

Injections, Intravenous Medication Errors Guideline Adherence Information Science

## STUDY PROTOCOL

# 1 INTRODUCTION

#### 1.1 Background

There is little previous research investigating tools for preparing and testing technical information about medicines aimed at health professionals: only one study has been identified, which applied systematic user testing to improve the presentation of the Summary of Product Characteristics for two medicines.

A considerable number of studies have been carried out in the related fields of patient medicines information and clinical guideline production. In these areas, systematic user testing has been shown to improve understanding and decrease reading time. Recently published guidance on the implementation of clinical guidelines recommends user testing and it is required in the development of patient information leaflets for licensed medicines. User testing is therefore considered the current "gold standard" method for improving patient information and the presentation of information to clinical guideline committees.

The major advantage of user testing is that it is based on potential users reading the document to locate key information and correctly use it to recommend appropriate actions and the reasons for them. Problems and potential solutions are therefore identified. Iterative rounds of interviews with potential users are followed by document revision, until all problems are resolved. Each interview involves direct questions to determine whether the interviewee can locate and use key points of information, followed by a semi-structured interview to explore opinions of more general issues (e.g. structure of the document, language used). This ensures that participants only give feedback once they have experience of using a document to locate information.

During phase 1 (described in a previous protocol), this study investigated the application of user testing to the NHS Injectable Medicines Guide (IMG). Standard user testing methodology was applied to revise the adult IMG monograph for a high-risk medicine. The "users" during this process were hospital and community nurses who regularly prepared and administered intravenous medicines.

In phase 2 (described by this protocol), the outcomes achieved as a result of user testing will be investigated, by measuring the effect of this process on the occurrence of injectable medicine preparation and administration errors in a randomised *in situ* simulation experiment carried out with hospital nurses on duty in their usual clinical environment.

## 1.2 Rationale

Medication errors are a serious and persistent problem in all healthcare systems. The number of reported errors has increased year-on-year, to more than 100,000 in England and Wales. A review of reports between 2005 and 2010 found that 17% of errors resulted in patient harm, including 822 cases of death or severe harm. The incidence of errors is higher for injectable medicines, with systematic reviews suggesting an error rate of 35-50%. In November 2016, an alert was issued

highlighting 2200 reports since 2013 of incidents with just one intravenous medicine (phenytoin), resulting in four deaths, five cases of severe harm and 121 cases of moderate harm.

In 2007, the National Patient Safety Agency required healthcare providers to provide protocols for the administration of injectable medicines, such as the NHS Injectable Medicines Guide (IMG). This is used by nurses in more than 125 hospitals to guide the administration of individual doses and is accessed more than 1.5 million times per year. Such guidance must be written carefully, as difficulty finding relevant, unambiguous information in technical documents has been linked to serious medication errors. Systematic reviews of factors contributing to patient safety incidents therefore include contradictory, incomprehensible or poor quality information. It is therefore concerning that the IMG has been described as too detailed and confusing to likely users. This suggests that improvements to the presentation of the information in the IMG might result in fewer errors. Such concerns are shared by the IMG advisory board ([name], IMG Project Manager, personal communication, 28/10/2016).

The IMG is therefore the ideal case study to use to investigate the wider question of whether improved written documents providing technical information to health professionals can reduce the incidence of medication errors.

As has already been discussed, systematic user testing is the gold standard approach for improving the quality of written documents. However, the effect of user testing medicines information on the behaviour of readers has not been previously investigated, as the previous studies outlined above have measured outcomes such as understanding and reading time. This study will therefore add to the understanding of the outcomes achieved by user testing, by measuring the effect of this process on the occurrence of injectable preparation and administration errors.

We will compare error rates occurring during use of the user tested monograph and the original IMG monograph. This is an appropriate comparator as it was this version of the IMG which was used as the starting point of the user testing process. In addition, this version of the IMG represents current standard practice in many NHS hospitals. This comparator will therefore enable the research to determine whether the user testing process results in fewer injectable preparation and administration errors, and whether the user tested monograph results in fewer errors than the current standard IMG guide.

## 1.3 Research Question

Research question (whole study): Is it possible to reduce the incidence of medication errors by improving the content, wording, structure and formatting of written documents providing technical information to health professionals?

This question will be investigated using the NHS IMG as a case study relating to one of the highest risk routes of medicines administration.

## 1.4 Objectives

Objectives for the entire study are:

- 1. To identify and resolve problems in a typical NHS Injectable Medicines Guide (IMG) monograph using systematic user testing.
- 2. To compare the rates of preparation and administration errors associated with use of the original and user testing developed IMG monograph.
- 3. To determine whether systematic user testing of the IMG is a cost-effective approach to improving patient safety.
- 4. To advise the IMG Advisory Board on generic lessons learned during user testing which could be introduced to the entire guide during the next revision cycle.

Only objective 2 will be addressed during phase 2 of the study (this protocol).

## 1.5 Study design

This study will be a single-blind, randomised parallel group *in situ* simulation experiment with a 1:1 allocation ratio. It is designed to determine whether the user tested guide is superior to the original guide.

*In situ* simulation involves a simulated episode of patient care integrated into a clinical environment with participants who are on duty health professionals. It is therefore useful in patient safety research if it is not feasible to test interventions during routine patient care, while still allowing participants to experience the time pressures and distractions present in the clinical environment.

During the simulation, each participant will prepare an infusion of an intravenous medicine ("bathicillin") in response to a simulated inpatient medication order for an adult. They will then administer this dose to a training manikin arm. During this process, they will be observed by a researcher, who will note any preparation or administration errors.

One group will use the "original" IMG monograph to guide this process and the other group will use the "user tested" IMG monograph. The groups will be treated identically in all other respects. As cross-over design will not be utilised, as this would create a serious order effect.

# 2 METHODS: PARTICIPANTS, INTERVENTIONS, DEFINITIONS AND OUTCOMES

## 2.1 Study setting

This study will be multi-centre and will take place in at least three hospitals, to increase the generalisability of the results. Any hospital in England that employs nurses who meet the participant inclusion and exclusion criteria (Section 2.2) will be eligible to be a study site. All sites will carry out the same activities, namely recruiting participants and hosting the *in situ* simulation.

# 2.2 Eligibility criteria

#### 2.2.1 Inclusion criteria

- Qualified nurse or midwife registered with the Nursing and Midwifery Council
- Authorised to prepare and administer intravenous medicines in a hospital
- Has prepared and administered intravenous medicines during at least 50% of working shifts during the past six months (or since authorisation to prepare and administer intravenous medicines if this was granted more recently)
- At the time of data collection, actively working as a nurse in clinical area at usual hospital

#### 2.2.2 Exclusion criteria

• Participated in phase 1 (user testing) of this study

#### 2.3 Interventions

Participants will be allocated either the monograph revised via a user testing methodology (the "user tested monograph") or the "original monograph". Both monographs will give guidance on the intravenous administration of the same high-risk medicine (voriconazole). However, to prevent participants using prior knowledge of this medicine, both monographs will be "anonymised" by changing any mention of the medicine's generic name to "bathicillin". In addition, brand names will be changed to invented names. References to the use of an infusion pump will be removed, as such equipment may not always be readily available in study areas.

With the exception of the anonymisation described above, the "original monograph" will be identical to the IMG monograph in use at the start of phase 1 (user testing) of this study.

The "user tested monograph" will be the final result of the user testing carried out in phase 1 of this study. This process started with the "original monograph", which was then revised through three iterative cycles of identifying and resolving problems with the document by obtaining feedback from nurses as they used the document to locate and apply key information. Both monographs will therefore include the same content, but it will be presented differently.

In a survey of NHS organisations that use the IMG in clinical areas (carried out as part of the development of this protocol), 72 of 91 of responding organisations (79%) used the IMG mainly or entirely on computer screen. Therefore, the allocated monograph will be provided to the participants on a laptop computer screen at the start of the *in situ* simulation.

There will be no criteria for discontinuing or modifying the allocated monograph for any participant.

## 2.4 Definitions

An error will be considered to be any deviation in the preparation or administration of bathicillin from the simulated medication order, the hospital's intravenous drug administration policy and guidelines, or the IMG monograph. Participants will not be required to assess the clinical appropriateness or

legal validity of the medication order. As this is a simulation study, deviations from procedures designed to reduce the likelihood of a subsequent error will not be considered. In line with other recent studies, examples of such procedural deviations include tubing not being tagged and labelled in accordance with local policy and failure to document administration of bathicillin in line with hospital policy. In addition, errors relating to the safe handling of sharps will not be considered.

An "IMG-related error" will be an error in a process that requires use of information from the IMG. This does not mean that the error was definitely caused by the IMG, but the IMG had the potential to influence it. All other errors will be classified as "non-IMG-related errors".

Table 1 shows the definitions of error types that will be used in this study and whether they are classified as "IMG-related errors" or "non-IMG-related errors". These error types were developed by combining the typologies employed in previous research and the requirements of national guidelines. Certain types of error (e.g. omitted dose, wrong patient) are not included in Table 1, as they are not relevant to this study, due to the investigation of a single dose of one simulated medicine administered at a single time point.

Error type	Definition	Error code
IMG related errors -	- an error in a process that requires use of information from the IMG	
Wrong reconstituting fluid	The dose is reconstituted with a different fluid to that specified in the IMG monograph	11
Wrong reconstituting fluid volume	The dose is reconstituted with a volume of fluid which differs from that specified in the IMG monograph by ≥10%	12
Dose discrepancy	The administered dose differs from the prescribed dose by ≥5% a	13
Wrong diluent	The dose is infused in a different diluent to that specified in the IMG monograph	14
Wrong diluent volume	The dose is infused in a different volume of diluent to that specified in the IMG monograph	15
Incorrect technique (IMG related)	The dose is prepared or administered in a way that does not meet the requirements specified by the IMG monograph, e.g. the vial is shaken when the monograph specifies "do not shake".	16
Wrong route	The dose is administered via a different route to that specified on the medication order	17
Flush error	The intravenous cannula is not flushed in accordance with hospital policy before administration of the dose. (Any requirements for a flush after administration are not relevant, as the infusion will not be observed for its entire duration).	18
Rate discrepancy The dose is administered at a rate that differs from that specified in the IMG monograph by $\geq 10\%$		19
Infusion expiry error	An infusion is labelled with an expiry date and time that is not in accordance with the IMG monograph	110

Table 1: definitions of error types and categorisation as "IMG-related errors" or "non-IMG-related errors"

Other IMG related	Any IMG related error which does not fit one of the above categories	111
error	Any line related error which does not in one of the above categories	

Non-IMG-related errors – an error in a process that did not require use of information from the IMG		
Wrong medication	A different medication to that specified on the medication order is administered	N1
Incorrect technique (non-IMG related)	The dose is prepared or administered in a way that does not meet the requirements of hospital policy, e.g. incorrect mixing technique, air in the syringe, where these details are not specified in the IMG monograph.	N2
Non-aseptic technique	Breach of the aseptic technique policy of the hospital during the preparation or administration of the dose (e.g. hands not washed, vials/additive ports not swapped with an alcohol wipe)	N3
Expired ingredients	Use of expired medicine, reconstituting fluid, diluent or flush.	N4
Other non-IMG related error	Any non-IMG related error which does not fit the above categories	N5

aA figure of 5% has been deliberately chosen, to ensure that an error is recorded when the participant does not account for the displacement value. This was a common error during the user testing phase. A threshold of 5% has been used in a number of previous studies.

The potential clinical significance of all observed errors will be scored and then classified as minor, moderate or severe, using the expert panel method described in sections 4.1 and 4.3

## 2.5 Outcomes

#### 2.5.1 Primary outcome

The primary outcome will be the observed rate of IMG-related moderate-severe errors in each group. Following the approach of recent meta-analyses, error rates will be expressed as percentages using the number of doses considered to have one or more errors as the numerator and the total number of doses as the denominator.

#### 2.5.2 Secondary outcomes

There will be a number of secondary outcomes:

[figure not shown]
- The rate of IMG-related errors of any severity in each group
- The rate of moderate-severe non-IMG-related errors. This outcome will be measured because it is hypothesised that a more easily understood IMG monograph will enable participants to concentrate more on other aspects of the injection preparation and administration process.
- The rate of non-IMG-related errors of any severity in each group
- The mean time taken to prepare and administer the dose for each group. For each participant, the time will be measured from the point at which they start to read the simulated medication order or IMG monograph until the point at which they inform the observer that they would leave the simulated patient's bedside with the infusion running. This outcome will be measured

because it is hypothesised that a more easily understood IMG monograph will be read and interpreted more quickly, thus reducing the time required to prepare and administer the dose.

- The mean modified Decision Conflict Score (mDCS) for each group. This will be calculated from participant's responses to a modified Provider Decision Process Assessment Instrument (mPDPAI) immediately after they have finished preparing and administering the intravenous infusion. The mDCS is a measure of participants' degree of knowledge and uncertainty whilst making decisions during the preparation and administration of the medicine. It will be measured because it is hypothesised that a more easily understood IMG will result in participants having great confidence in the decisions made during the dose preparation and administration process.
- The mean monograph preference score of each group. Immediately after completing the mPDPAI, each participant will be shown the version of the IMG monograph they did not use to prepare the dose of medicine and asked to rate their preferred version using a seven point Likert scale. This will be measured because it is hypothesised that participants will prefer the more easily used IMG.

# 2.6 Participant timeline

All study procedures will take place sequentially on the same day:

#### 2.7 Sample size

There is one published study that reports the rate of moderate to severe errors in the preparation and administration of intravenous medicines to adults on UK hospital wards and which used the same error observation and severity determination techniques as this study. This study observed one or more moderate-severe errors in 30% of 430 intravenous doses. If the definitions to be used for the current study had been applied in this previous research, 27.2% of 430 intravenous doses would have involved one or more moderate-severe IMG-related errors.

Using the same techniques, a larger and more recent, but as yet unpublished study, observed one or more moderate-severe preparation errors in 28% of 1148 adult injectable medicine doses administered on UK hospital wards. This study did not investigate administration errors, but their inclusion would have increased this error rate.

These error rates are supported by other studies, which either took place in other countries or used different severity determination methods, which report similar rates of moderate-severe preparation and administration errors (22-34% of doses).

Therefore, it is reasonable to assume that participants in the "original monograph" group will make at least one moderate-severe IMG-related error in 30% of doses.

Following discussion with the Study Advisory Group, it was agreed that at least one moderate-severe error occurring in 15% of doses would represent a clinically relevant reduction. This is in line with the assumptions underlying other recent research considering the effect of educational interventions on the rate of injectable medicine preparation and administration errors.

Standard calculations indicate that a sample size of 121 participants per group will give an 80% probability of detecting this reduction in the moderate-severe error rate at the 5% significance level, assuming equal group size. This assumes that there is no clustering of the data by hospital site, as NHS hospitals are required to provide similar training for staff preparing and administering intravenous medicines, and to follow similar procedures.

A power calculation accounting for clustering (using STATA) indicates that a sample size of 43 participants per group per cluster will give an 80% probability of detecting the above reduction in the moderate-severe error rate at the 5% significance level. This assumes an intraclass correlation coefficient of 0.01, which is low, but justifiable given the similarities in nurse training and procedures discussed above. As it is anticipated that four hospitals is the most likely number of study sites, this equates to a sample size of 172 participants per group.

Given that likely recruitment rates are not accurately known, this study will therefore achieve a minimum sample size of 121 participants per group, but may increase this up to 172 participants per group if recruitment is sufficiently quick. This larger sample size would provide greater power to analyse the effect of hospital site (and other variables, see Section 4.3) on the outcomes.

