# 3 METHODS: ASSIGNMENT OF INTERVENTIONS

## 3.1 Sequence generation

The allocation sequence will be generated using an online blocked randomisation list generator (www.sealedenvelope.com/simple-randomiser/v1/lists). A block size of 10 will be employed. Allocation will be stratified by research site and nursing experience, to ensure equal representation of nurses employed by different hospitals and with different levels of experience in each group.

Nursing experience will be measured by the total number of years each participant has been accredited for the administration of intravenous medicines, with two strata: <5 years and ≥5 years. A cut off of five years of experience preparing and administering intravenous medicines was chosen because evidence suggests that the number of errors with which a nurse is involved decreases over the first four to six years of their nursing experience. In particular, one study found that the risk of intravenous medicine administration errors decreased with each year of a nurse's experience up to six years.

The allocation sequence will link each participant's unique randomisation code to their allocation groups: A or B.

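### The clustered sample size (172 per group for 80% power) is calculated as if hospitals were randomised; with nurses randomised within hospital, 172 per group gives about 92% power and 121 already gives about 80%

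*Protocol*

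**What the plan says.** All the sample size statements are in section 2.7 of the protocol.

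- **Rates.** Participants using the original monograph "will make at least one moderate-severe IMG-related error in 30% of doses". For the user-tested monograph, "at least one moderate-severe error occurring in 15% of doses would represent a clinically relevant reduction".
- **Unclustered size.** At the 5% level, "a sample size of 121 participants per group will give an 80% probability of detecting this reduction". The text adds: "This assumes that there is no clustering of the data by hospital site".
- **Clustered size.** With an intraclass correlation of 0.01, "a sample size of 43 participants per group per cluster will give an 80% probability". For the four hospitals expected, "this equates to a sample size of 172 participants per group".
- **Use of the two figures.** The minimum is 121 per group. The study may go up to 172 if recruitment is fast enough, and the section notes that the larger size would help in analysing hospital site and other variables. The Study Summary gives the range as "121-172 participants per group".

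On allocation, section 1.5 describes a parallel-group experiment with a 1:1 ratio. Section 3.1 says "Allocation will be stratified by research site and nursing experience" and ties each participant's own code to group A or B. Section 3.3 has participants, not hospitals, assigned to groups. Section 4.3 compares the error rates by chi-squared test and then by a mixed logistic model with hospital as the random effect.

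**The concern.** The usual design effect, 1 + (m − 1) × ICC, applies when everyone in a cluster receives the same allocation. Differences between clusters then become part of the difference between arms. Here every hospital contributes to both arms in near-equal numbers, so a hospital with a generally high or low error rate shifts both arms together. Section 2.7 appears to use the first formula for the second design.

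What is at stake is the accuracy of the power statement for the primary outcome and the reason given for the upper end of the recruitment range. On the section's own cluster logic, the guaranteed minimum of 121 per group would fall well short of 80% power. A reader could therefore wrongly think that the minimum trial is too small once clustering is admitted.

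**Working it through.** **Inputs (section 2.7):** p1 = 0.30, p2 = 0.15, 5% significance, 80% power, ICC ρ = 0.01, K = 4 hospitals. Whether the test is one- or two-sided is not stated; two-sided reproduces 121, whereas one-sided would give 95.

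**1. Unclustered size.** With pooled p = 0.225:

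n = [1.96 √(2 × 0.225 × 0.775) + 0.8416 √(0.30 × 0.70 + 0.15 × 0.85)]² / 0.15² = (1.1575 + 0.4889)² / 0.0225 = 120.5, rounded up to 121.

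This matches the protocol. Power at 121 is 80.2%.

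**2. The protocol's clustered size.** In a cluster-randomised trial with K clusters in each arm and m participants per cluster, K m = n [1 + (m − 1)ρ], so

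m = n(1 − ρ) / (K − nρ) = 120.47 × 0.99 / (4 − 1.2047) = 42.67, rounded up to 43, and 4 × 43 = 172.

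Both figures match exactly. As a check, the design effect is 1 + 42 × 0.01 = 1.42, the effective size is 172 / 1.42 = 121.1, and power is 80.2%. The protocol does not print its formula, so its use is inferred from this agreement. The formula implies four separate clusters in each arm, eight in all.

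**3. The minimum size on that same logic.** m = 121 / 4 = 30.25; design effect 1 + 29.25 × 0.01 = 1.2925; effective size 93.6; power about 69%.

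**4. The design as described.** Let r be the correlation between a hospital's effect in one arm and its effect in the other. The variance of the difference between arms, relative to no clustering, is

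(1 − ρ) + mρ(1 − r).

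With a treatment effect common to all hospitals, r = 1 and the factor is 0.99. With r = 0 it becomes 1 + (m − 1)ρ, the cluster-trial formula.

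| Per group | No design effect | Factor 0.99 |
|---|---|---|
| 121 | 80.2% | 80.6% |
| 172 | 91.8% | 92.1% |

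The size needed for 80% power is 120.47 × 0.99 = 119.3 with the factor and 120.5 without it.

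**5. Simulation.** 40,000 trials were simulated with four hospitals, a site effect shared by both arms, ICC 0.01 and a chi-squared test. Power was 80.0% at 120 per group and 92.0% at 172. With ICC 0.05, power at 172 was still about 91%.

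**6. Sensitivity to the base rate.** Section 2.7 also gives 27.2% as the rate of moderate-severe IMG-related errors when this study's definitions are applied to the earlier UK study. For 27.2% versus 15% at 172 per group:

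z = [0.122 √172 − 1.96 √(2 × 0.211 × 0.789)] / √(0.272 × 0.728 + 0.15 × 0.85) = (1.600 − 1.131) / 0.5705 = 0.82, which is power of about 79%.

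**The case against.** Four points can be made for the protocol.

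- **The error is on the safe side, and 172 is optional.** This stands. The commitment is to 121 per group, and the increase depends on recruitment speed. The section also gives a second reason for the larger number, the analysis of site and other variables. A reader might infer that up to 2 × (172 − 121) = 102 extra nurses would be recruited only to restore power that was never lost. The text does not say that.

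- **The 121-per-group statement is correct.** This stands too. A reader might infer that both power statements are wrong. Only the 80% attached to 172 is wrong; the sentence about no clustering beside 121 is a needless condition on a correct figure.

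- **Cancellation needs a similar effect in every hospital.** This stands as a condition. Section 4.3 expects earlier use of the guide to influence the size of the effect, and such use may differ between hospitals. The protocol gives no figure for treatment-by-hospital variation, so r is an assumption here. With ICC 0.01 and four hospitals, power for r = 1, 0.75, 0.5 and 0 is 92%, 89%, 86% and 80% at 172, and 81%, 78%, 75% and 69% at 121. The stronger claim that no design effect could ever apply is therefore not supported. Equally, the protocol's figure needs r = 0, meaning that a hospital's two arms are no more alike than two different hospitals. The protocol neither states nor argues for this, and the random hospital effect in section 4.3 does not describe it.

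- **The 92% depends on the 30% base rate.** This stands. At 27.2% versus 15% it is about 79%. That is a reason to want the larger trial, but it is not a clustering adjustment and does not make the stated calculation right.

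**Conclusion.** The concern holds for one figure. The clustered calculation in section 2.7 belongs to a trial that randomises hospitals, whereas sections 1.5, 3.1 and 3.3 randomise nurses within hospitals. For 30% versus 15%, two-sided 5%, ICC 0.01 and a treatment effect common to all hospitals, 172 per group has about 92% power. The stated 80% is too low by about 12 percentage points, and 80% power after allowing for site needs about 120 to 121 per group. The direction is conservative: at the stated rates neither end of the range is underpowered. The error lies in the stated power and in the reasoning for the upper limit; randomisation, outcome, primary test and minimum size are unaffected.

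**What to change.** Reword section 2.7:

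- Remove the cluster-trial inflation, and the sentence that makes 121 per group depend on no clustering by hospital.
- State that nurses are randomised individually, stratified by hospital, and that, assuming a similar effect across hospitals, 121 per group gives about 80% power and 172 per group about 92% for 30% versus 15%.
- Justify the upper end of the range by the reason already in the section, the analysis of site and other variables. If wished, add the lower base rate of 27.2%, at which 172 per group gives about 79% power against 15%.

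The range in the Study Summary can stay. The cost is a few sentences, with no additional participants and no change to design or analysis.
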